9.2 Immunogenicity Assessments

An overview of the timing of blood sample collection for immunogenicity assessment is provided in Table 1.

Unused samples may be used for assay validation and additional studies of the mechanism of action of the vaccine.

If a subject receives a licensed/authorized vaccine, no further immunogenicity samples will be collected/analyzed after receipt of the licensed/authorized vaccine. Immunogenicity samples on Day 393 will only be collected from subjects who attend this visit at the site,

ie, subjects who received the Day 180 booster AND who had not received a licensed/authorized vaccine before this visit.

9.2.1 Humoral Immune Response

The humoral immune response elicited by the vaccine will be evaluated by measurement of SARS-CoV-2 spike protein-specific antibodies in serum by ELISA and SARS-CoV-2 neutralizing antibodies in serum by an activity assay.

In addition to evaluation of vaccine-induced immune responses, ELISA to SARS-CoV-2 N-antigen (not contained in the vaccine construct) will be performed to determine the subject's serology status to natural infection, to retrospectively identify the baseline serology status, and to detect and/or confirm natural infection during the trial. The SARS-CoV-2 N-antigen ELISA will be performed at the specified time points for humoral immune response testing to SARS-CoV-2 S-protein.

Seroconversion will be defined as:

- Subjects seronegative at baseline (in addition to a negative serostatus at baseline, such subjects would also not have been exposed to SARS-CoV-2 during the trial before the applicable sample was collected, as confirmed by a titer increase in antibodies to SARS-CoV-2 N-antigen or a RT-PCR-positive swab during the trial): an increase in antibody titer against SARS-CoV-2 spike protein versus baseline.
- Subjects seropositive at baseline: a 2-fold increase in antibody titer against SARS-CoV-2 spike protein versus baseline.

To further evaluate the humoral immune response, cross-reactivity with other viral antigens might be analyzed.

9.2.2 Cell-Mediated Immunity

CMI will only be evaluated in approximately 20 subjects per CVnCoV group at assigned site(s).

The frequency and functionality of SARS-CoV-2 spike-specific T-cell response after antigen stimulation will be determined in PBMC in comparison to baseline. For example, ICS to investigate Th response will be used to investigate whether vaccination induces a Th1 shift from baseline. Further T-cell immune response may be investigated with other technologies like ELISpot or CyTOF.

9.2.3 Innate Immune Response

The innate immune response will only be evaluated in approximately 20 subjects per CVnCoV group at assigned site(s) by measuring serum cytokines, including but not limited to IFN- α , IFN- γ , IL-6, CCL 2, and IP 10.

9.3 Laboratory Testing for COVID-19 Disease

As a baseline assessment, a RT-PCR test for SARS-CoV-2 will be performed in all subjects. Testing will be done for SARS-CoV-2 spike protein to evaluate vaccine-induced immune responses as well as for SARS-CoV-2 N-antigen (not contained in the vaccine construct) to evaluate immune responses induced by natural infection. This will allow to retrospectively define the subject's serology status, including the baseline status for the by-group/cohort analysis.

Subjects will be prompted once or twice per week to report if the subjects have any of the following symptoms: cough, shortness of breath, difficulty breathing, fever $\geq 37.8^{\circ}\text{C}$, fatigue, myalgia, chills, wheezing, nasal congestion, runny nose, sore throat, headache, diarrhea, or new olfactory and taste disorders.

A COVID-19 symptoms log listing these symptoms will be provided to subjects with RT-PCR-confirmed COVID-19 disease (refer to Appendix 4 for an example symptom log).

If any of these symptoms are observed, the Investigator will collect appropriate samples as soon as feasible and locally perform RT-PCR and/or serological assays as locally available to evaluate for infection with SARS-CoV-2. If a serological assay is performed, this should look at antibodies against N protein antigen, but not to antibodies against Spike viral antigen, as this is part of the vaccine. These assays will be repeated 7 to 14 days after the initial assessment.

Any subject with clinical suspicion of SARS-CoV-2 infection will undergo appropriate testing and referral within the local healthcare system as appropriate. Subjects with confirmed SARS-CoV-2 infections during the trial should not receive any additional vaccine dose, but will be closely monitored for disease patterns and severity. In order to assess severity of disease, subjects will document disease progression on a symptom log and Investigators will document additional clinical parameters based on hospital records, if applicable.

The currently available case definition for COVID-19 disease is provided in Appendix 5.

10 STATISTICAL CONSIDERATIONS

Due to the exploratory nature of this trial, only descriptive statistics will be used. No confirmatory statistical inference will be performed.

10.1 Sample Size Determination

The sample size of the trial ensures that sufficient safety and immunogenicity data will be available for the selected CVnCoV dosage(s) prior to initiation of Phase 3 clinical trials. Approximately 200 subjects will be enrolled in the initial phase to investigate different dose levels and 20 subjects as control. Furthermore, 440 subjects will be enrolled in an expansion phase (400 will receive CVnCoV and 40 the active control).

Table 5 Sample Size

Open-label	Randomized										
	Dose escalation ^a	Group 1 6 µg Age 18-60	Group 2 6 µg Age >60	Group 3 12 µg Age 18-60	Group 4 12 µg Age >60	Expansion Age 18-60	Expansion Age >60	Total CVnCoV	Group 5 Active control Age 18-60	Group 6 Active control Age >60	Expansion Active control Age ≥18
4	11	12^c	90	90	200	200	603	10^b	10^b	40	

a. Only if the dose level was previously untested.

b. Includes 1 control subject from Group 1 and 1 control subject from Group 2.

c. Includes the 4 subjects from the dose escalation.

The trial is designed to provide a reasonable precision for an estimate of the number of subjects with seroconverting for nCoV spike protein antibodies and an acceptable rate of Grade 3 adverse reactions. Table 6 provides the estimate and 95% credibility interval for the observed numbers of subjects with seroconverting for nCoV spike protein antibodies for different sample sizes assuming a Beta (1.9,0.1) prior for seroconverting for nCoV spike protein antibodies and a Beta (0.5,1.5) prior for Grade 3 adverse reactions.

Table 6 Estimate of Number of Subjects with Seroconverting for nCoV Spike Protein Antibodies and 95% Credibility Interval

Rate (%)	Sample Size					
	90		200		603	
	N	95% CI	N	95% CI	N	95% CI
80	72	80.3 (71.7 - 87.7)	160	80.1 (74.4 - 85.3)	482	80 (76.7 - 83.1)
85	76	84.7 (76.7 - 91.2)	170	85.1 (79.9 - 89.7)	513	85 (82.2 - 87.8)
90	81	90.1 (83.3 - 95.3)	180	90 (85.6 - 93.8)	543	90.1 (87.6 - 92.3)
95	86	95.5 (90.5 - 98.7)	190	95 (91.6 - 97.6)	573	95 (93.2 - 96.6)
100	90	99.9 (98.9 - 100)	200	100 (99.5 - 100)	603	100 (99.8 - 100)

CI: credibility interval; N: subjects with seroconverting for nCoV spike protein antibodies

Table 7 provides probabilities (in %) that the following 2 conditions are simultaneously met for assumed true adverse reaction rates and for assumed true rates with seroconverting for nCoV spike protein antibodies and for different sample sizes:

- there is a $\geq 80\%$ probability that the true rate of Grade 3 AR(s) is $\leq 33\%$, and
- there is a $\geq 90\%$ probability that the true rate of subjects seroconverting for nCoV spike protein antibodies $> 95\%$.

For example, for a sample size of 200, assuming a true adverse reaction rate of 20% and a true rate of subjects seroconverting for nCoV spike protein antibodies of 97.5%, the 2 conditions are met with a probability of 76%.

Table 7 Probabilities (in %) for Assumed True Adverse Reaction Rates and for Assumed True Rates of Subjects with Seroconverting for nCoV Spike Protein Antibodies and Different Sample Sizes

	Sample Size								
	90			200			603		
	True rate of subjects with seroconverting for nCoV spike protein antibodies (%)			True rate of subjects with seroconverting for nCoV spike protein antibodies (%)			True rate of subjects with seroconverting for nCoV spike protein antibodies (%)		
True adverse reaction rate (%)	95	97.5	100	95	97.5	100	95	97.5	100
5	17	61	100	12	76	100	10	98	100
10	17	61	100	12	76	100	10	98	100
15	17	61	100	12	76	100	10	98	100
20	16	60	98	12	76	100	10	98	100
25	14	51	83	12	73	96	10	98	100
30	8	28	46	7	41	54	8	78	79
35	2	8	13	1	6	8	0	3	3

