## 12.0 Statistical Methods

Due to the exploratory nature of this trial, only descriptive statistics will be used. No confirmatory statistical inference will be performed.

All data collected during this study will be displayed in data listings, unless otherwise specified. Data listings will be sorted by dose level and subject identifier. Screening failures will be excluded from all listings and tables if not otherwise stated. Listings will include all relevant assigned/derived variables.

Unless otherwise noted, categorical variables will be summarized using counts and percentages. Descriptive statistics (mean, median, standard deviation (SD), Q1, and Q3, minimum and maximum values) for continuous variable will be presented. Mean, median, Q1 and Q3 will be presented to 1 decimal more than original data. SD will be presented with 2 decimals more than original data. Minimum and maximum will match the decimal points in the original data. Maximum number of decimals will be 4, unless otherwise stated.

Expansion for subjects 18 to 60 years of age may start once the final dose for subjects in this age category has been selected based on the data from Trial CV-NCOV-001. Expansion for subjects >60 years of age may start once the final dose for these subjects has been selected based on data from this trial. Subjects enrolled in the expansion cohorts will be handled in the same manner as subjects in the first phase of the study.

The analysis will be presented in the following manner if not otherwise stated:

- Age; Overall age, age 18-60 and age >60 (61 years or older),
- Dose; any, dose 1, dose 2, booster doses at day 57 and day 180
- CVnCoV, active control (hepatitis A vaccine, or pneumococcal vaccine), and total.

Subjects in the expansion cohorts will be presented together with subjects from the initial phase of the trial.

All data summaries and tabulations will be prepared using SAS Version 9.4 or higher.

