## 12.8.2 Analysis Solicited AEs

The following summaries of solicited AEs within 7 days after each trial vaccination and within 7 days after any trial vaccination will be provided:

- Summary of solicited AEs, local AEs and systemic AEs, overall and by maximum grade
  - will also be presented by sex (female/male) for any dose, dose 1, dose 2 and booster dose regardless of retrospective serology status at baseline.
- Occurrence of local AEs, overall and by maximum grade
- Occurrence of systemic AEs, overall and by maximum grade
- Occurrence of related systemic AEs, overall and by maximum grade (mild / moderate / severe)
- Duration (days) of solicited AEs, overall and for grade 3 events
- Duration (days) of local AEs, overall and for grade 3 events
- Duration (days) of systemic AEs, overall and for grade 3 events
- Duration (days) of related systemic AEs, overall and for grade 3 events
- Daily summary of local AEs (only for each dose)
- Daily summary of systemic AEs (only for each dose)
- Daily summary of related systemic AEs (only for each dose)
- Summary of time of onset (Day) for grade 3 solicited AEs, any solicited AEs, local, systemic AEs, and related systemic AEs
- Time of onset (Day) of local AEs
- Time of onset (Day) of systemic AEs
- Time of onset (Day) of related systemic AEs
- Number and percentage of subjects with solicited Grade 3 adverse reaction(s) or SAEs considered as related to the trial vaccine according to the Investigator with the 95% credibility interval based on the Beta (0.5, 0.5) prior distribution for each dose level and dose will be calculated and summarized.
- Individual solicited local and systemic adverse events will be displayed in by-subject figures
- Individual grade 3 solicited local and systemic adverse events will be presented in a figure.

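### The two-part posterior rule that supports the sample size is never evaluated in the analysis, and the planned Grade 3 reaction line counts a narrower event than the protocol defines.

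*Protocol*

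**What the plan says.** **Sizing.** Protocol 10.1, repeated in SAP 8.5.1, gives two supports for the sample size. The first is precision: Protocol Table 6 (SAP Table 3) shows 95% credibility intervals for seroconversion. The second is a joint rule: Protocol Table 7 (SAP Table 4) "provides probabilities (in %) that the following 2 conditions are simultaneously met for assumed true adverse reaction rates". The conditions are P(Grade 3 adverse reaction rate ≤33%) ≥80% and P(seroconversion rate >95%) ≥90%. The priors are given as "assuming a Beta (1.9,0.1) prior for seroconverting for nCoV spike protein antibodies and a Beta (0.5,1.5) prior for Grade 3 adverse reactions". The worked example takes n=200, a 20% reaction rate and 97.5% seroconversion, and concludes that "the 2 conditions are met with a probability of 76"%.

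**Analysis.** For reactions, SAP 12.8.2 plans a number and percentage "with the 95% credibility interval based on the Beta (0.5, 0.5) prior distribution for each dose level and dose". It counts subjects with solicited Grade 3 adverse reactions or related SAEs. For seroconversion, SAP 9.4 and 12.9.1 plan an estimate and 95% credibility interval under Beta(1.9,0.1), plus an exact Clopper-Pearson interval. SAP 10.5.10 builds the credibility interval from the 2.5% and 97.5% beta quantiles. SAP 12.0 adds: "Subjects in the expansion cohorts will be presented together with subjects from the initial phase of the trial".

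**Definition of the event.** Protocol 9.1.6, and SAP 11.2 with it, define Grade 3 adverse reactions as related Grade 3 events that are solicited systemic, solicited local or unsolicited. The matching analysis line in Protocol 10.3.5.1 carries no restriction to solicited events.

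**The concern.** The sizing sections set limits (33% and 95%) and required posterior probabilities (80% and 90%). None of these reappears in Protocol 10.3.5 or in SAP 9.4, 10.5.10, 12.8.2 or 12.9.1, and SAP 6.1 does not say that the rule was for planning only. The trial report would therefore not say whether the conditions were met.

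Two things make this more than a missing line. First, the word solicited in SAP 12.8.2 removes subjects whose only Grade 3 reaction was unsolicited. The planned rate is then not the rate to which the 33% limit refers, and it can be lower. Second, a reader with only a 95% interval will naturally look at whether it clears 95% or 33%. That is a stricter test than the design used, so the reader could conclude that a target was missed when the design's own condition was met. If the probabilities are worked out later without pre-specification, the prior, reaction definition, visit and pooling would be chosen with the data in view.

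**Working it through.** **Inputs.** From Protocol 10.1: n=200, true reaction rate 20%, true seroconversion 97.5%, priors Beta(0.5,1.5) for reactions and Beta(1.9,0.1) for seroconversion. From SAP 12.8.2: Beta(0.5,0.5) for reactions in the analysis. Reactions and seroconversion are taken as independent; the documents do not state this, but Table 7 reproduces under it to within 2 percentage points.

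**Step 1: reproduce the 76%.** With x reactors, the posterior is Beta(x+0.5, 200−x+1.5). P(rate ≤33%) is 0.829 at x=60 and 0.787 at x=61, so at most 60 reactors are allowed. With y seroconverters, the posterior is Beta(y+1.9, 200−y+0.1). P(rate >95%) is 0.872 at y=193 and 0.935 at y=194, so at least 194 are needed.

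- P(X≤60 | 200, 0.20) = 0.9997
- P(Y≥194 | 200, 0.975) = 0.7641
- Product = 0.7638, or 76.4%, against the stated 76%

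The plan's figure is correct for the rule as written.

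**Step 2: effect of the changed reaction prior.** Under Beta(0.5,0.5) the n=200 cut-off is still 60. At n=90 it moves from 26 to 25, at n=290 from 89 to 88, and at n=580 from 182 to 181. The change is at most one subject at these sizes.

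**Step 3: the planned seroconversion interval against the design condition (n=200).**

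| Seroconverters | P(rate >95%) | Design condition (≥90%) | Planned 95% credibility interval |
|---|---|---|---|
| 193 | 0.872 | not met | 93.5% to 98.6% |
| 194 | 0.935 | met | 94.2% to 98.9% |
| 195 | 0.972 | met | 94.9% to 99.2% |
| 196 | 0.990 | met | 95.6% to 99.4% |

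At 194 and 195 the condition is met but the interval includes 95%. With a true rate of 97.5%, the chance of one of these two counts is P(Y≥194) − P(Y≥196) = 0.7641 − 0.4383 = 0.3258, about 33%.

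**Step 4: the pooled 12 µg groups.** Pooling the phases gives 90+200 = 290 per age group and 2×290 = 580 overall; neither size is in Table 7. At n=290 the rule allows at most 89 reactors and needs at least 280 seroconverters. With the same true rates it is met with probability 88.6%. Counts of 280 and 281 show the same disagreement with the interval, with probability 0.8855 − 0.6973 = 0.188. At n=580 the rule (at most 182 and at least 558) is met with probability 97.8%.

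**Step 5: the event counted.** The rule and Protocol 9.1.6 count any related Grade 3 event, solicited or not. SAP 12.8.2 counts solicited Grade 3 reactions or related SAEs. A subject with a related, non-serious, unsolicited Grade 3 event and no solicited Grade 3 reaction counts in the first and not in the second. As a hypothetical case at n=200, 59 subjects with solicited Grade 3 reactions and 2 more with only such an unsolicited event make 61 under the rule (not met) but 59 in the SAP line. The documents give no expected frequency for these events, so the actual shortfall cannot be sized.

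**The case against.** The strongest reply is that the trial is declared descriptive in Protocol 10 and SAP 12.0, and neither document calls the rule a success criterion. The precision support in Table 6 does carry through: SAP 9.4 and 12.9.1 plan the same kind of interval under the same Beta(1.9,0.1) prior. The seroconversion probability can be worked out from the reported count. Related unsolicited Grade 3 events are tabulated separately under SAP 12.8.1, and all adverse events are listed, so no data are lost. All of this stands. It makes the matter a gap between planning and reporting, not a fault in the sample size. It does not answer the narrowed reaction count: that line departs from the protocol's definition, and separate tables do not show how many subjects had either kind of event.

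A reader might go further and infer that the true probability behind the 76% is 43%. That figure arises if the reaction interval must lie at or below 33% and the seroconversion interval wholly above 95%: at most 53 reactors and at least 196 seroconverters at n=200, so 0.9897 × 0.4383 = 0.434. The documents do not support it as a correction. Nowhere do they compare a 95% interval with either limit, and the calculation replaces the stated 80% and 90% by 97.5% on each endpoint. The choice of interval is also arbitrary: requiring the planned exact interval for seroconversion instead gives about 26%.

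**Conclusion.** The point holds as a reporting gap of moderate weight. The 76% is correct, and the sample size is not called into question. What is missing is any output that evaluates the two-part rule, and the reaction line in SAP 12.8.2 measures a narrower event than the protocol's Grade 3 adverse reaction, so its rate can be lower than the one the 33% limit is about. The change of reaction prior is an inconsistency with little effect.

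The planned intervals do not replace the rule. For seroconversion they disagree with the design condition at two counts at n=200 (probability about 33%) and at two counts at n=290 (about 19%), given a true rate of 97.5%. These figures rest on full evaluable numbers; the seroconversion denominators may be smaller, because subjects with undetermined serostatus are left out of the counts (SAP 10.6.3) and booster recipients are censored and also presented separately (SAP 12.9.1). The 88.6% and 97.8% at the pooled sizes are context only and do not justify the sample size after the fact.

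**What to change.** 1. In SAP 12.8.2, count all related Grade 3 adverse reactions as Protocol 9.1.6 defines them, including unsolicited events. If the composite with related SAEs is kept, show the Grade 3 reaction count on its own line, since that is what the rule uses.
2. In SAP 12.8.2 and 12.9.1, for the 12 µg group by age and overall, report P(Grade 3 reaction rate ≤33%) under Beta(0.5,1.5) and P(seroconversion >95%) under Beta(1.9,0.1) beside the intervals. Take seroconversion at Day 43, and state which doses the reaction count covers, because the rule does not say. Label both as descriptive summaries and show the 80% and 90% planning thresholds next to them.
3. Do not apply the rule to the 6 µg groups of 11 and 12; Table 7 does not cover those sizes. Figures for n=290 and n=580 may be added as context if wanted, but not as sample size justification.

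The cost is a corrected event flag, two beta distribution function calls and one small table. No new data are needed.

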10.2 Populations for Analyses

Safety Set

The safety set will consist of all subjects who received at least 1 dose of trial vaccine and for whom any post-vaccination safety data are available.

Immunogenicity Set

The immunogenicity set will include all subjects who received at least 1 dose of trial vaccine and for whom the baseline blood sample and at least 1 additional blood sample are available for analysis.

In case a dose level has not been previously administered in Trial CV-NCOV-001, a dose-determining set (DDS) is defined and will consist of 4 additional subjects in the respective dose level and will be part of the safety set, who have either experienced Grade 3 adverse reactions or SAEs considered as related to the trial vaccine according to the Investigator at any time during the first 24 hours, or completed the 24-hour observation period without experiencing Grade 3 adverse reactions or SAEs considered as related to the trial vaccine according to the Investigator. The DDS will be used to confirm the safety on untested dose level prior to enrollment into the randomized part at the particular dose level. The minimum vaccination and safety evaluation requirements will have been met if the subject has received the planned dose of CVnCoV, has been observed for at least 24 hours following the first vaccine administration and has completed the required safety evaluation. Subjects who do not meet these requirements will be regarded as ineligible for inclusion in the DDS. Since DDS is only used to confirm safety prior to randomization, the DDS is not reported in the tables but Grade 3 adverse reactions and SAEs considered as related to the trial vaccine according to the Investigator used for the analyses are marked in the listings.

10.3 Statistical Analyses

10.3.1 General Considerations

All data obtained in this trial and documented in the eCRF will be listed and summarized with sample statistics or frequency tables as appropriate. In all tables, listings and figures, the dose groups will be reported from the lowest to the highest dose and by age group. The safety and immunogenicity analyses will be done overall and by baseline serology status for SARS-CoV-2.

The primary and secondary objectives and endpoints related to seroconversion for SARS-CoV-2 spike protein and SARS-CoV-2 neutralizing antibodies will, in addition to the immunogenicity set, be analyzed for subjects who:

- Received dose 1 and dose 2 of trial vaccine.
- Have baseline and Day 43 blood samples for immunogenicity assessment.
- Have no major protocol deviations expected to impact the immunogenicity outcomes.

A statistical analysis plan (SAP) will be prepared and finalized at the latest prior to database lock. This document will provide further details regarding the definition of analysis variables and analysis methodology to address all trial objectives and the handling of missing data.

Data on COVID-19 cases from this trial may be pooled with data from other trials investigating CVnCoV such as Trials CV-NCOV-004 and CV-NCOV-005.

